**A. SPECIFIC AIMS**

*List the broad, long-term objectives and the goal of the specific research proposed, e.g., to test a stated hypothesis, create a novel design, solve a specific problem, challenge an existing paradigm or clinical practice, address a critical barrier to progress in the field, or develop new technology.*

**This study aims to evaluate the effectiveness of transcranial direct current stimulation (tDCS) and a brief cognitive intervention in increasing pain tolerance. Specifically, this study will determine whether healthy subjects will indicate greater pain tolerance to a heat stimulus following a single 20-minute session of anodal vs. cathodal tDCS (compared to sham tDCS). This study will also test whether providing one of four cognitive pain-managament interventions (conducted during the tDCS session) will result in even greater pain tolerance among subjects who also received tDCS .**

**B. BACKGROUND AND SIGNIFICANCE**

*Briefly sketch the background leading to the present application, critically evaluate existing knowledge, and specifically identify the gaps that the project is intended to fill. State concisely the importance and health relevance of the research described in this protocol by relating the specific aims to the broad, long-term objectives. If the aims of the study are achieved, state how scientific knowledge or clinical practice will be advanced.*

**Recently, the use of low amplitude direct current stimulation of the human cortex has received attention as a possible treatment for pain (Been et al, 2007). This technique (called transcranial direct current stimulation or tDCS) involves the placement of two sponge electrodes over separate areas of the scalp. tDCS has been shown to be capable of changing the excitability of the superficial neurons immediately**

beneath the sponge electrodes. Evidence suggests that anodal stimulation is associated with increased cortical excitability and cathodal stimulation is associated with decreased cortical excitability (Been et al., 2007). The electrodes can therefore be placed on the scalp according to the desired part of the cortex with which to excite.

Across experimental and clinical studies, investigators have demonstrated the analgesic effects that tDCS can have in the experience of pain (see Fregni et al., 2007 for a review). The dorsolateral prefrontal cortex (dIPFC) is one area of the brain that may be particularly relevant in using tDCS to reduce perceived pain and increase pain tolerance. For example, in a study of patients who had undergone ERCP surgery (Borckardt et al., 2011a), there was a significant decrease in reported pain scores and in medication use among the patients who received tDCS. The dIPFC appears to affect emotional aspects of the pain experience and one's perceived controllability of pain (Boggio et al., 2008; Borckardt et al., 2011b), and this may be one way that tDCS affects changes in pain perceptions when anode currents are directed at the dIPFC.

There is also extensive research to support the use of cognitive-behavioral therapy (CBT) in the treatment of pain conditions (e.g., Chen et al., 2004; McCracken & Turk, 2002; Morley et al., 1999). It is well established that CBT is effective in greatly reducing the suffering that patients with chronic pain endure. There are three main elements to CBT for chronic pain, which include education about how emotions and behaviors can affect one's experience of pain, training in coping strategies to better manage the pain experience (including both behavioral and cognitive strategies), and assistance in the maintenance of those coping strategies (Kerns et al., 2011). Providing accurate information about one's pain experience and training individuals to think about their pain experience in a different way is one relevant aspect of pain treatment that may relate to activity of the prefrontal cortex.

Despite all of the evidence promoting the use of CBT in treating pain conditions, many individuals still do not benefit from this kind of intervention (Kerns et al., 2011), and it is possible that the use of tDCS over the dIPFC may enhance the potential benefit of cognitive interventions in treating pain. The goal of this study is to investigate how both tDCS and a brief cognitive intervention affect pain tolerance in an experimental setting, and specifically whether the combination of tDCS and a cognitive intervention will enhance pain tolerance. Ultimately, we hope our results will further support the use of tDCS for therapeutic applications in the area of pain management, as well as provide initial evidence of its benefit in combination with cognitive-based treatments for pain that are already in use.

### **C. PRELIMINARY STUDIES**

*Provide an account of the principal investigator's preliminary studies pertinent to this protocol and/or any other information that will help to establish the experience and competence of the investigator to pursue the proposed project.*

The investigators have conducted multiple studies using tDCS technology that have already demonstrated the benefit of tDCS in increasing pain tolerance and threshold (see Borckardt et al., 2011a, 2011b as examples). The proposed study will be the first to combine tDCS and a cognitive intervention element, although we expect no complications or safety issues with our use of tDCS or cognitive intervention for pain in this study.

### **D. RESEARCH DESIGN AND METHODS (including data analysis)**

*Describe the research design and the procedures to be used to accomplish the specific aims of the project. Explain sequentially the study procedure, including all the visits, contacts, and interactions. If the study will be designed in phases and each phase will require separate IRB approval, please specifically indicate this in the description. Include how the data will be collected, analyzed, and interpreted and specify what statistical methods will be used. Discuss the particulars of the research instruments, questionnaires and other evaluation instruments in detail. For well known, established valid and reliable test instruments the detail here can be brief. If interviews or groups settings are to be audio taped or video taped describe in detail the conditions under which it will take place. Describe any new methodology and its advantage over existing methodologies. Discuss the potential difficulties and limitations of the proposed procedures and alternative approaches to achieve the aims. As part of this section, provide a tentative sequence or time-table for the project. Point out any procedures, situations, or materials that may be hazardous to personnel and the precautions to be exercised.*

**PARTICIPANTS:**

Subjects will be 360 healthy adult volunteers. Subjects will be between the ages of 18 years and 75 years recruited from the greater Charleston area via flyers and newspaper advertisements. Subjects will be paid for their participation.

**Laboratory Pain Assessment:**

Participants will undergo quantitative sensory testing to measure pain threshold. Ten randomly ordered warming (5) and cooling (5) sequences will be administered with variable (2-10 sec random) lead times and a warm/cool rate of 0.2° C per sec until the subject indicates that a temperature change was perceived. **THERMAL PAIN THRESHOLD ASSESSMENT:** Cutaneous heat and cold stimuli will be delivered via a Contact Heat-Evoked Potential Stimulator (CHEPS; Medoc, USA) attached to the volar forearm of each subjects left arm. The Method of Limits will be used. The thermode will heat/cool at a rate of 0.5° C per second until the subject indicates that pain was perceived. The procedure will be repeated 10 times (5 hot and 5 cold) and mean values will be used. **THERMAL PAIN MAGNITUDE ESTIMATION:** Twelve separate 2-second thermal stimuli (4 stimuli each at 46°, 47.5°, 49° C; randomized) will be applied to each subject's left volar forearm. The target temperature will be sustained for 2 seconds and the thermode will immediately cool to 32° C. After termination of each stimulus, subjects will rate both the intensity and the unpleasantness of the stimulus using the computerized VAS. **THERMAL WIND-UP PAIN ESTIMATION:** The CHEPS will be used to deliver 20 very brief noxious thermal stimuli to the left volar forearm of subjects at the rate of 1 stimulus (0.75 sec duration) every 1.5 seconds (at 49°C) thus facilitating C-fiber activation and receptive field expansion of the WDR neurons in the dorsal horn. Subjects will continuously indicate level of pain intensity using a dynamic computerized VAS. **MECHANICAL PAIN THRESHOLD ASSESSMENT:** The IITC Life Sciences Digital Anesthesiometer will be used to apply pressure to the dorsal surface of the distal phalange of the digit minimi of the left hand. Pressure will be increased at the rate of 10 grams per second. Participants will stop the stimulus when pressure reaches the pain threshold and the pressure will be recorded in grams.

**tDCS:**

A single 20-minute tDCS session will be conducted with the Phoresor-II Auto (Model PM850, Iomed, Salt Lake City Utah, USA) using 2.0mA current. Electrodes will be 4x4 cm sponge electrodes soaked in sterile saline. The anode will be placed over the left prefrontal cortex (F3 from the EEG 10-20 system) located via the Beam F3 measurement system. The cathode will be attached to the right shoulder. For sham tDCS, cathode to anode stimulation will be for the duration of the 20-minute session. The current density and total charge delivered by the above parameters is consistent with those used safely in the current research literature on tDCS. Participants will be given vitamin-E cream to apply to the scalp following tDCS to reduce possible skin irritation.

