**STUDY DESIGN AND PROCEDURES:**

Interested participants will call and be pre-screened on the telephone. If interested participants meet the inclusion criteria they will be scheduled for one appointment (lasting approximately 1 hour). Upon coming to the Brain Stimulation Laboratory for the appointment, participants will review and sign the informed consent document. Written informed-consent will be obtained by one of the study investigators or the study coordinator. Participants will complete the Center for Epidemiological Studies 10-item depression scale (CESD), the Beck Anxiety Inventory (BAI), the Reiss-Epstein-Gursky A.S.I., and the Brief Pain Inventory (BPI).

After completing the initial questionnaires they will be taken to the laboratory where they will undergo five trials of the heat tolerance laboratory pain test. The tDCS electrodes will then be placed and fastened with Velcro straps, and the tDCS session will be started. During the tDCS stimulation, participants will undergo the cognitive or educational component of the study as well as pain tolerance assessment procedures every 5 minutes. Patients will randomly receive one of four cognitive behavioral therapy interventions administered through headphones so that the research staff can remain blind. The four cognitive behavioral therapies include Pain-Catastrophizing Cognitive Intervention, Cognitive-Behavioral Distraction Intervention, Cognitively-Mediated Relaxation Intervention, Education-Only Control Condition.

After completion of the tDCS session, participants will again undergo five consecutive trials of the quantitative sensory testing.

At the completion of each appointment participants will be assessed for adverse effects of the stimulation, and they will be asked if they think they received real or fake stimulation and will rate how confident they are in their answer using a 0-10 scale (0= guessing 10= absolutely sure). Participants will also be asked to complete a short supplemental form at the end of the appointment. Participants will also be compensated \$40 in cash at that time for their participation in the study.

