**ANALYSIS:**

3 variable MANCOVA will be used to investigate whether change scores (from pre- to post-stimulation) in pain tolerance ratings (i.e., the temperature that participants were no longer able to tolerate the heat stimulus) are significantly affected by stimulation condition. Anodal, Cathodal, and Sham stimulation will be randomly paired with one of the four cognitive behavioral therapies. Both the stimulation and cognitive behavioral therapy will be run through a randomized computer system so as to maintain blinding. A 4X3X2 [CBT group BY tDCS group BY time (pre-post)] mixed multiple analysis of covariance (MANCOVA) will be conducted with the multiple QST values as dependent measures and while controlling for physiological indices across phases (pre- and post-intervention. Gender, age, and race will be controlled in all analyses, although specific demographic variable differences are not expected for the present study. Scores on initial tests (i.e., CESD, BAI, and BPI) may also be examined as control variables

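### The sham instruction, read literally, delivers current for the whole session, and the cathodal arm is never set up, so the plan has no usable inert control

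*Combined protocol and SAP*

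**What the plan says.** Section A (Specific Aims) sets the first question as a "single 20-minute session of anodal vs. cathodal tDCS (compared to sham tDCS". The Analysis part of section D confirms three stimulation levels: "Anodal, Cathodal, and Sham stimulation will be randomly paired with one of the four cognitive behavioral therapies". Under Study Design and Procedures, participants are questioned at the end of the visit: "they will be asked if they think they received real or fake stimulation". All three statements need a sham condition that differs from both active ones.

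The tDCS paragraph of section D is the only place that describes delivery. It specifies a single 20-minute session at 2.0 mA with 4x4 cm electrodes and one montage: "The anode will be placed over the left prefrontal cortex" and "The cathode will be attached to the right shoulder". On sham it says only: "For sham tDCS, cathode to anode stimulation will be for the duration of the 20-minute session". It gives no ramp-down, early switch-off, zero-current step or separate amplitude for sham.

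The cathodal arm has no stated electrode sites, polarity, current or duration anywhere. Section B says only what the two polarities are thought to do: "anodal stimulation is associated with increased cortical excitability and cathodal stimulation is associated with decreased cortical excitability".

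**The concern.** A sham arm is there to show what happens without effective current. The sentence that defines it here prescribes stimulation for the full session. If staff follow it, the sham arm receives an active condition. One of the two planned contrasts with sham is then an active arm compared with itself, and the other is a comparison of opposite polarities. Neither can be read as active against inert.

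The blinding check fails as well: nobody would have received fake stimulation, so for no participant would that answer be correct. None of this can be repaired in the analysis, because it depends on what was delivered.

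**Working it through.** **Possible meanings of the sham sentence**

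1. Polarity is reversed relative to the stated montage, at the paragraph's 2.0 mA. Sham then duplicates cathodal stimulation.
2. The stated montage is used. Sham then duplicates anodal stimulation.
3. The sentence is a mislabelled description of the cathodal arm. Sham is then not described at all.

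The documents do not settle which was meant. None of the three gives the operator a usable sham procedure.

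**Dose.** The plan gives 2.0 mA, 20 minutes and 4 x 4 = 16 cm². That 2.0 mA also applies to sham is an inference: it is the only current given, and it is not broken down by arm.

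- Charge: 0.002 A x 1,200 s = 2.4 C
- Current density: 2.0 mA / 16 cm² = 0.125 mA/cm²

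On meanings 1 and 2 the sham dose would therefore equal the active dose.

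**Participants affected.** The plan gives 360 participants and a 4 x 3 between-subject layout. Equal allocation is assumed, not stated: 360/12 = 30 per cell and 360/3 = 120 per stimulation arm, so the sham arm is 4 cells of 30.

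**What the contrasts estimate.** Let anodal stimulation change tolerance by +a SD, and cathodal by −b SD, relative to no current.

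| What sham receives | Anodal − sham | Cathodal − sham | Anodal − cathodal |
|---|---|---|---|
| No effective current | a | −b | a + b |
| Meaning 1 (as cathodal) | a + b | 0 | a + b |
| Meaning 2 (as anodal) | 0 | −(a + b) | a + b |

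Anodal against cathodal is unaffected, provided a cathodal arm is really delivered. Only the comparisons with sham are lost.

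**Illustrative size.** The plan states no alpha, power, effect size or SD, so it has no figure of its own to reproduce. The values below assume 120 per arm and a two-sample t-test at two-sided 5%, and ignore the covariates and the cognitive-intervention factor. Rejection rates by standardised difference are:

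- 0: 5%
- 0.2: 33.9%
- 0.4: 87.0%
- 0.6: 99.6%
- 0.8: over 99.9%

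Substituting these into the contrasts gives (anodal−sham / cathodal−sham):

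| Assumed a, b | Inert sham | Meaning 1 | Meaning 2 |
|---|---|---|---|
| 0.4, 0.4 | 87% / 87% | >99% / 5% | 5% / >99% |
| 0.4, 0.2 | 87% / 34% | >99% / 5% | 5% / >99% |
| 0.4, 0 | 87% / 5% | 87% / 5% | 5% / 87% |
| 0.4, −0.4 | 87% / 87% | 5% / 5% | 5% / 5% |

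In the first two rows, the contrast that is not null is inflated because it adds the two polarity effects, while the other is null by construction. In the last row both polarities raise tolerance equally, and that real effect is missed on both contrasts.

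**The case against.** The strongest reply is that this is a drafting slip. The sentence reads as if a word is missing, and a dropped word could reverse its meaning; loss in text extraction cannot be excluded either. The aims, the blinding question and the analysis all point to an intended, distinct sham, and nothing suggests that the investigators chose an active one. The Analysis section also says that stimulation runs through a randomised computer system, so delivery may not depend on staff interpreting this sentence. The consent pages are not available and might describe sham.

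Much of this is fair. A slip is the likeliest explanation, and meaning 2 is the weakest of the three, since reversed wording is an odd way to describe the montage just given. The power figures rest wholly on assumptions, say nothing about meaning 3, and show no loss in one case (a = 0.4, b = 0 under meaning 1).

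Still, intent stated elsewhere does not tell an operator what to do, and the computer system's settings per arm are not given. Even if a word was dropped, the printed text supplies no sham procedure. The cathodal arm remains without a set-up on every account except meaning 3, and there sham has none.

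**Conclusion.** The concern holds. The protocol as written either gives the sham arm full-session current or leaves sham undefined, and it does not separately set up the cathodal arm. Followed literally, the text cannot deliver the comparison with sham in section A; the anodal-against-cathodal part survives if a cathodal arm is really delivered.

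This conclusion rests on the text alone and needs none of the power figures. The affected arm of 120 participants assumes equal allocation, the matching sham dose of 2.4 C assumes that 2.0 mA applies to sham, and the rejection rates are illustrations under assumed effects. The point must be corrected because the control condition for the first aim depends on it.

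**What to change.** Rewrite the tDCS paragraph of section D with one line per arm:

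- **Anodal:** anode at F3, cathode on the right shoulder, 2.0 mA, 20 minutes.
- **Cathodal:** the reversed montage at the same dose, if that is what the sentence was meant to say.
- **Sham:** a procedure that does not deliver current for the full session, with electrode sites, current and switch-off time chosen and stated by the investigator.

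If this is a wording error, the cost is one paragraph, with no extra participants or procedures.

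If full-session current in the sham arm is truly intended, also restate the aims in section A, the real-or-fake question in Study Design and Procedures and the arm labels in Analysis as polarity comparisons without an inert control, and limit the conclusions accordingly. That too needs no extra participants.

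If anyone has already been run, first record what the sham arm actually received.

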**STUDY DESIGN AND PROCEDURES:**

Interested participants will call and be pre-screened on the telephone. If interested participants meet the inclusion criteria they will be scheduled for one appointment (lasting approximately 1 hour). Upon coming to the Brain Stimulation Laboratory for the appointment, participants will review and sign the informed consent document. Written informed-consent will be obtained by one of the study investigators or the study coordinator. Participants will complete the Center for Epidemiological Studies 10-item depression scale (CESD), the Beck Anxiety Inventory (BAI), the Reiss-Epstein-Gursky A.S.I., and the Brief Pain Inventory (BPI).

After completing the initial questionnaires they will be taken to the laboratory where they will undergo five trials of the heat tolerance laboratory pain test. The tDCS electrodes will then be placed and fastened with Velcro straps, and the tDCS session will be started. During the tDCS stimulation, participants will undergo the cognitive or educational component of the study as well as pain tolerance assessment procedures every 5 minutes. Patients will randomly receive one of four cognitive behavioral therapy interventions administered through headphones so that the research staff can remain blind. The four cognitive behavioral therapies include Pain-Catastrophizing Cognitive Intervention, Cognitive-Behavioral Distraction Intervention, Cognitively-Mediated Relaxation Intervention, Education-Only Control Condition.

After completion of the tDCS session, participants will again undergo five consecutive trials of the quantitative sensory testing.

At the completion of each appointment participants will be assessed for adverse effects of the stimulation, and they will be asked if they think they received real or fake stimulation and will rate how confident they are in their answer using a 0-10 scale (0= guessing 10= absolutely sure). Participants will also be asked to complete a short supplemental form at the end of the appointment. Participants will also be compensated \$40 in cash at that time for their participation in the study.

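### Pain tolerance readings taken during stimulation, the only ones made while tDCS and the cognitive intervention run together, have no planned analysis

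*Combined protocol and SAP*

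**What the plan says.** Section D, tDCS: "A single 20-minute tDCS session will be conducted". Section D, Study Design and Procedures, sets out three measurement periods:

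- Before stimulation: "five trials of the heat tolerance laboratory pain test".
- During stimulation: the "cognitive or educational component of the study as well as pain tolerance assessment procedures every 5 minutes". The number of trials at each of these tests is not given.
- After stimulation: "participants will again undergo five consecutive trials of the quantitative sensory testing".

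The Analysis paragraph names two things for tolerance: change scores from before to after stimulation, and a mixed MANCOVA set out as "4X3X2 [CBT group BY tDCS group BY time (pre-post" (closing brackets omitted here). Its time factor has two levels. Baseline tolerance is not among the listed covariates. No outcome, summary or model refers to the in-session readings, and no rule for missing data is stated.

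The Specific Aims place the tDCS comparison after the session. They also ask whether a cognitive intervention delivered during the session raises tolerance further in people who receive tDCS, and fix no time point for that second question.

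**The concern.** Up to 360 people undergo repeated painful testing during stimulation, and the plan does not say what the results are for. These are the only readings made while both interventions are running, so they bear directly on one reading of the combined-effect aim. Without a named analysis, someone could later choose among the time points after seeing the data, or the readings could go unreported.

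The analysis that is named also gives up some precision. In a two-time-point model, the group-by-time effect is a comparison of change scores. With randomised groups, using the baseline as a covariate estimates the same post-session contrast with smaller variance whenever the pre-post correlation is below 1.

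**Working it through.** **Inputs.** From Section D: "Subjects will be 360 healthy adult volunteers"; "Anodal, Cathodal, and Sham stimulation will be randomly paired with one of the four cognitive behavioral therapies"; a 20-minute session; tolerance tested every 5 minutes; five trials before and five after. The plan gives no standard deviation, correlation, effect size, alpha or power, so it has no figure of its own to reproduce. The correlations below are assumptions, shown as ranges. All comparisons are variance ratios at the same group sizes, so the allocation ratio, which is not stated, does not enter.

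**Number of in-session tests.** Every 5 minutes over 20 minutes gives three to five readings, depending on whether minutes 0 and 20 count. I use four (20/5) and show three and five as a check.

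**1. Post-session contrast: baseline as covariate against change score.** Take unit variance before and after, with correlation ρ between the two analysed values.

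- Change score variance: 2(1 − ρ)
- Baseline-adjusted variance: 1 − ρ²
- Ratio: (1 + ρ)/2, so the reduction is (1 − ρ)/2

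| ρ | Change score | Adjusted | Reduction |
|---|---|---|---|
| 0.5 | 1.00 | 0.75 | 25% |
| 0.7 | 0.60 | 0.51 | 15% |
| 0.8 | 0.40 | 0.36 | 10% |

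**2. On-stimulation average against post-session mean.** Let single trials have unit variance and a common correlation r, within and between periods. The mean of k trials has variance Vk = (1 + (k − 1)r)/k. Assume the pre-session and post-session values are five-trial means; the plan states averaging for pain threshold but not for tolerance. After adjustment for the five-trial baseline:

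- Post-session mean: V5 − r²/V5
- Four in-session tests of one trial each: V4 − r²/V5
- Four in-session tests of five trials each: V20 − r²/V5

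For r = 0.7: V5 = 0.760, V4 = 0.775, V20 = 0.715 and r²/V5 = 0.49/0.76 = 0.645.

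| r | Post-session | In-session, single trials | Ratio | In-session, five trials each | Ratio |
|---|---|---|---|---|---|
| 0.5 | 0.183 | 0.208 | 1.14 | 0.108 | 0.59 |
| 0.7 | 0.115 | 0.130 | 1.13 | 0.070 | 0.61 |
| 0.8 | 0.078 | 0.088 | 1.13 | 0.048 | 0.62 |

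So the variance of the on-stimulation average is about 13% higher with single trials and 38% to 41% lower with five trials each. At r = 0.7, three single-trial tests give V3 − r²/V5 = 0.800 − 0.645 = 0.155 (35% higher), and five give V5 − r²/V5 = 0.115 (no difference). With five trials each, three tests give 0.075 (35% lower) and five give 0.067 (42% lower).

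**3. How the two sets of assumptions relate.** In step 1, ρ is the correlation between the values analysed. In step 2, r is between single trials. If the step 2 model held exactly, the correlation between five-trial means would be r/V5: 0.5/0.6 = 0.83, 0.7/0.76 = 0.92 and 0.8/0.84 = 0.95. The step 1 reduction would then be 8%, 4% and 2%. Trials within one period are probably more alike than trials across periods, which would lower ρ. The range in step 1 is therefore conditional on ρ and shrinks as ρ approaches 1.

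**The case against.** The strongest reply is that the plan is coherent as it stands. The tDCS aim is set after the session, the analysis matches it, and in-session readings reflect partial exposure: at minute 5 a participant has had a quarter of the stimulation. That is right as far as it goes. It supports keeping the post-session contrast primary and treating the on-stimulation average as a separate estimand. It does not explain why data relevant to the combined aim have no stated analysis.

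Several stronger readings are tempting, and the documents do not support them.

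- *The in-session data would sharpen the main result considerably.* With a mixed model of the kind proposed and complete data, the post-session contrast is essentially the baseline-adjusted one. The in-session values help it mainly when post-session values are missing. Any large gain belongs to the on-stimulation average, and it reverses if each in-session test is a single trial.
- *Anyone with one missing value is dropped.* That is a common software default for a MANCOVA, but the plan states no such rule. Assuming 12 outcomes at two times and 1% independent missingness gives 360 × 0.99²⁴ = 283 retained. The number of outcomes is not listed, though, and missing values in a single visit of about an hour would probably cluster in the same people. Tolerance alone needs two values: 360 × 0.99² = 353.
- *The least tolerant participants are lost because they stop early.* The Analysis paragraph defines tolerance as the temperature at which the participant can no longer bear the heat. Stopping early is a low value, not a missing one.
- *These are the best data on the combined effect.* That is a judgement; the aims fix no time point for the combination.
- *They are the only tolerance data after baseline.* The post-session block is labelled quantitative sensory testing, and the Laboratory Pain Assessment section describes no tolerance procedure. But that block is introduced as a repeat, and the Analysis paragraph uses pre-to-post tolerance change, so post-session tolerance was evidently intended. It is likewise an inference, though a reasonable one, that the in-session test uses heat.

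**Conclusion.** The point holds in a limited form. Tolerance is measured during stimulation, the analysis has no place for those readings, and the aims ask about the combination that only those readings observe in progress. This is worth correcting before analysis, but it does not invalidate the planned post-session comparison.

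The gain for the primary contrast comes from baseline adjustment and is modest: 10% to 25% of variance for an assumed ρ of 0.8 to 0.5, and less if five-trial means correlate more strongly. The on-stimulation secondary could be somewhat less precise than the post-session mean or clearly more so. The deciding quantity, trials per in-session test, is not in the documents. These figures assume equal variances, a common trial correlation and, for the second comparison, averaging over trials. They compare precision only, and do not assume that the effect during stimulation equals the effect afterwards.

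**What to change.** For tolerance, replace the change-score analysis and pre-post MANCOVA with a linear mixed model:

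- Outcomes: tolerance at each in-session test and after the session.
- Covariate: baseline tolerance, with the demographic covariates already planned.
- Fixed effects: tDCS group, cognitive intervention group, time and all their interactions.
- Within-person covariance: unstructured.
- Population: all randomised participants with any post-baseline tolerance value, so that handling of missing values is explicit.
- Primary: the post-session tDCS contrast.
- Named secondary, as a separate estimand: the average on-stimulation contrast, for the tDCS main effect and for tDCS by cognitive intervention.

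State the number and timing of the in-session tests, the trials at each, and how trials are combined. Say explicitly that the in-session and post-session blocks include heat tolerance, if that is what is meant. If the sponsor does not want the secondary, the minimum is to label the in-session readings exploratory.

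The cost is analysis wording and a standard mixed-model program, with no new data. The downside is one more pre-specified secondary estimate and reliance on a covariance model.
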